With the continuous development and clinical popularization of invasive blood pressure monitoring technology (ABP), the safety of patient anesthesia has been greatly guaranteed. The radial artery is superficial, and the forearm has a dual blood supply to the radial and ulnar arteries, thus becoming an arterial puncture

The first choice for catheterization.

It has been reported that the distal quarter of the forearm is the best insertion site for ultrasound-guided radial artery puncture, and the selection of the radial forearm catheterization improves the success rate and the overall success rate of the first puncture attempt

Prevalence of hematoma during the puncture process.

Invasive radial artery puncture sometimes cannot completely avoid complications, such as puncture hematoma and artery closure. Complications such as plug, infection, pseudoaneurysm, vasospasm, and neurovascular injury have been reported in the literature.

There are no recommendations for the best puncture site for radial artery puncture. Therefore, the choice is more appropriate and safe. Fully accurate location as ultrasound-guided radial artery puncture and catheterization is particularly important.

2. purpose of research

1. Main objective: To evaluate the anatomical parameters of the radial artery based on ultrasound imaging in the forearm,

Provide a reference to ultrasound anatomy for the clinical implementation of radial artery puncture.

2. Secondary objective: To find the best site of radial artery puncture to improve the safety and accuracy of radial artery puncture and catheterization.

3. Study design, methods, and study procedures

1. Study design

In this study, we plan to further compare the position distance between the radial artery and the ulnar artery, the vertical distance from the radial artery (center), and the distance between the radial artery (ulnar: radial)

The influence of age, BMI and left and right side on the radial artery position.

At the same time, the radial movement is intended to be guided by ultrasound at different distances during the radial artery puncture

Success rate of first puncture, puncture catheterization time, number of puncture and puncture related complications.

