The sample size of this study was calculated according to the results of the pretest. The main observation indicators were the vertical distance between the radial artery and the radial artery (radial artery), set statistical efficiency $1 - \beta = 0.9$, test standard $\alpha = 0.05$, $n = 30$, calculated $n = 30$, the case loss rate was set at 15%, and the final sample size was 100 example.

2. Research methods

The anatomical relationship and influencing factors of the radial artery were observed by ultrasound, and then the optimal puncture position was selected and the puncture was guided Reduce the number of punctures, reduce the complications, and improve the safety and precision.

3. Study steps

Main study steps: patients in the supine position, both upper limb abduction, palm up, wrist angle of 45°, using a portable ultrasound instrument (probe frequency 13–6 MHz, Sonosa), the ultrasound probe in the direction of the short axis in the radial artery (from the radial artery) to the radius for the projection of the radial artery, the relative distance of each anatomical site was 2cm. There was no significant compression of the radial artery to maintain the normal shape and site of the vessel. The radial diameter of the radial artery, the vertical distance from the skin, and the radial god were measured Distance relative to the radial artery (ulnar: radial). And recorded according to gender, age, BMI, and left and right sides.

Secondary study objective steps: the radial artery surface projection was divided into three sections. The first segment is in the

range of 0–5cm from the proximal to the radial stem, the second segment is in the range of 5–10cm from the proximal to the radial stem, and the third segment is in the range of 10cm to the proximal cubital fossa. And the puncture site was divided into the first stage of the left hand, the second section of the left hand, the third section of the left hand, the first section of the right hand, the second stage of the right hand, and the third section of the right hand; the experimenter randomly selected the puncture site, and used the portable ultrasound instrument (probe frequency 13–6 MHz, Sonos), and the in-plane puncture technique was used to puncture the radial artery, and the first puncture success rate, puncture insertion time and puncture times were recorded

And puncture-related complications.

4. Case selection

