1. Inclusion criteria: (1) patients undergoing elective surgery scheduled to undergo general anesthesia and invasive arterial blood pressure monitoring; (2) ASA grade I~; (3) age 18 to 65 years; (4) agree to participate in this clinical study and sign the informed consent form.

2. Exclusion criteria: (1) Allen positive or suspicious positive patients; (2) peripheral vascular diseases; (3) coronary artery related diseases; (4) local skin infection, rupture, scar and surgical history; (5) shock patients or acceptance, heart drugs, vasoreduction drugs; (6) peripheral nerve injury, anatomical abnormalities and neurological abnormalities; (7) upper limbs

The atic, not unable to complete the ultrasound assessment.

3. Termination criteria: Patients may withdraw their consent and withdraw from the trial at any time.

Any medical condition in the study that poses a risk that the continuing study subject may be terminated by the study physician

Continued to participate in this study;

And the study physician may terminate if the patient fails to comply with the study plan, or if a study-related injury occurs

Continue to participate in this study;

The investigator judged the other conditions that should be withdrawn from the trial.

5. Other alternative methods of diagnosis and treatment are available

If the radial artery puncture is unsuccessful, non-invasive blood pressure monitoring of the upper arm cuff is feasible.

Vi. Test items and test time points

After entering the patient into the room, the position distance between the radial artery (the radial artery, radial artery, radial artery, radial artery (center) vertical distance from the skin, and the distance of the radial nerve (ulnar: radial side) were measured. At the same time, the first puncture of radial artery puncture at different distances of the forearm was recorded

Power, puncture and catheterization time, number of puncture times, and puncture-related complications.

7. Efficacy evaluation criteria

Complete and accurately record all data, operation time, frequency and success rate.

Viii. Observation, recording and disposal of adverse events

You will be followed up and evaluated within 3 days of the study. In case of serious radial artery puncture complications during the experiment, the experiment will be stopped immediately, and the adverse events will be recorded and reported to the project leader. Positive and effective

Follow-up records according to the type of complications.

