IX. Research quality control and quality assurance

not have

X. Data security monitoring

The clinical study will develop a corresponding data safety monitoring plan according to the risk size. All bad events should be recorded in detail, properly handled and tracked until properly resolved or in stable condition, and timely submitted to the ethics committee and the competent department in accordance with the regulations. Door, sponsor and drug to report serious adverse events and unexpected events; principal investigator regularly

A cumulative review of all adverse events and an investigator meeting if necessary to assess the risks and benefits of the study; both Emergency unblinding may be performed when necessary to ensure subject safety and equity.

Xi. Statistical treatment

Using SPSS 22.0 software, the measurement data with mean \pm standard deviation ($\bar{x} \pm s$), ANOVA between groups; count data are presented as example or percentage, with t test, $P < 0.05$. The difference was statistically significant.

Xii. Ethics principles and requirements for clinical research

Clinical studies will follow the Declaration of Helsinki of the World Medical Congress and the Measures of the National Health and Family Planning Commission of the People's Republic of China, and implement informed consent,

Protect privacy, research free and compensation, risk control, special subject protection and compensation principles and requirements for research related damages. The clinical study was performed before EC approval of the study protocol. Before each subject is enrolled in the study, the Investigator has the responsibility to fully and comprehensively present the purpose, procedures and possible risks of the study, and their legal representative and to sign a written informed consent form that their participation in the clinical study is entirely voluntary, that they may refuse to participate or withdraw from the study at any stage of the trial without discrimination and retaliation, and their medical treatment and interests are not affected. The informed consent form should be kept as a clinical study document for future reference to effectively protect the personal privacy and data confidentiality.

Xiii. Research progress

July 2023–August 2023: Trial implementation

August 2023–March 2024: Collect and collate data

March 2024– June 2024: Writing the paper

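### The SAP's only rule for measurements, between-groups ANOVA, uses the wrong error term for ultrasound readings repeated across sites and arms of one patient

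*SAP*

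**What the plan says.** SAP section Xi (Statistical treatment) is a single short paragraph. For continuous data it specifies "the measurement data with mean \pm standard deviation ($\bar{x} \pm s$), ANOVA between groups". It names no repeated-measures ANOVA, mixed model, paired test or patient effect.

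The readings that this rule must cover are described under Study steps (section 3, item 3):

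- Position: "patients in the supine position, both upper limb abduction".
- Spacing of the measuring points along the artery: "the relative distance of each anatomical site was 2cm".
- Classification: "And recorded according to gender, age, BMI, and left and right sides".

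The measured items there are the artery diameter, its vertical distance from the skin and the nerve-artery distance. Section Vi confirms the last item: "the distance of the radial nerve (ulnar: radial side) were measured". Study design (section 3, item 1) lists the effect of left and right side on artery position among its comparisons. The main objective (section 2) is to "Provide a reference to ultrasound anatomy for the clinical implementation of radial artery puncture".

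**The concern.** If one patient supplies readings at several sites and on both arms, site and side are within-patient factors. The columns being compared are then not independent groups. Between-groups ANOVA treats them as if they were, so stable differences between patients (a deeper or wider artery throughout) are counted as noise. A within-patient analysis removes them.

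At stake is the anatomy table that serves the main objective. A modest real change along the forearm, or between arms, could be reported as no difference when the data already collected would have shown it. The point applies equally to diameter, depth and nerve distance.

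**Working it through.** **Inputs.** The SAP has no figure of its own for these comparisons to reproduce. It gives 100 patients, 15% loss and alpha 0.05, but not the number of sites, the within-patient correlation, an SD or an expected difference.

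- Evaluable patients: 100 × (1 − 0.15) = 85.
- Assumed: normal readings with SD 1; 3, 5 or 8 sites; correlation ρ of 0.3, 0.5 or 0.7, either equal between all sites or falling with distance (AR(1)); a steady drift of 0.3 SD from first to last site.

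**Step 1: why the error term is wrong.** With equal correlation, both methods use the same numerator. Its expected mean square under the null is σ²(1 − ρ). The repeated-measures error also estimates σ²(1 − ρ), so F is centred near 1. The between-groups error estimates σ², so F is centred near 1 − ρ: 0.7, 0.5 or 0.3. The test therefore rejects too seldom for any positive ρ.

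**Step 2: the signal available.** With 5 sites and a 0.3 SD drift, the site deviations are −0.15, −0.075, 0, 0.075 and 0.15. Their sum of squares is 2 × (0.0225 + 0.005625) = 0.05625, and 85 × 0.05625 = 4.78. The repeated-measures non-centrality is 4.78/(1 − ρ) = 6.8, 9.6 and 15.9 at ρ = 0.3, 0.5 and 0.7. It grows with ρ, and the between-groups test cannot use that gain.

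**Step 3: rejection under the null** (simulated, nominal 5%, 5 sites, ρ = 0.3/0.5/0.7).

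- Equal correlation: between-groups 0.90/0.13/0.00%; Greenhouse-Geisser 4.7/4.8/4.5%.
- AR(1): between-groups 2.9/1.5/0.5%; Greenhouse-Geisser 4.9/4.8/4.9%; uncorrected repeated measures 5.6/6.1/7.2%, which is why the correction is needed.
- Over all settings, between-groups rejects in 0.0% to 3.7%.

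**Step 4: power for a 0.3 SD drift** (between-groups v Greenhouse-Geisser, %; 20,000 runs for 5 sites, 10,000 for 3 and 8).

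| Sites, pattern | ρ = 0.3 | ρ = 0.5 | ρ = 0.7 |
|---|---|---|---|
| 3, equal | 34.4 v 53.1 | 30.2 v 68.6 | 22.9 v 89.4 |
| 3, AR(1) | 34.9 v 47.1 | 31.6 v 56.7 | 27.3 v 74.9 |
| 5, equal | 28.1 v 51.4 | 19.8 v 68.1 | 10.4 v 90.3 |
| 5, AR(1) | 33.1 v 39.8 | 28.7 v 44.1 | 23.4 v 54.5 |
| 8, equal | 27.2 v 55.0 | 16.3 v 72.8 | 6.2 v 94.5 |
| 8, AR(1) | 35.8 v 39.0 | 32.2 v 39.7 | 26.8 v 43.9 |

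The smallest gap is 39.0 − 35.8 = 3.2 points; the largest is 94.5 − 6.2 = 88.3 points.

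**Step 5: larger drifts.** At 0.6 SD (5, 8 and 10 sites, both patterns), between-groups ANOVA detects 88% to nearly 100%, against 95% to 100%. Setting by setting, the gap is about 1 to 8 points. At 0.8 SD both exceed 99%.

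**Step 6: left v right at one site, difference 0.3 SD.** The unpaired standard error is √(2/85) = 0.153, and 0.3/0.153 = 1.96, so power is near 50% whatever ρ is (simulated 49.9/49.1/49.0%). The paired standard error is √(2(1 − ρ)/85) = 0.128, 0.108 and 0.084, giving ratios of 2.3, 2.8 and 3.6. Simulated power is 63.9/78.4/94.6%.

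**The case against.** Four points can be made for the plan.

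1. **The sentence is generic and translated.** Section Xi names neither the ultrasound readings nor a site comparison, and its ANOVA wording may mean only that groups are compared. That every patient is scanned at every site and on both arms is inferred; abducting both arms is positioning, and recording by side could mean noting whichever side was scanned. This stands as a limit. Even so, measuring points 2 cm apart along one artery only make sense within a patient, and section Xi offers no other rule.

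2. **The error is conservative.** Correct: site and side comparisons carry no added false-positive risk. The cost is lost power only.

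3. **The loss depends on the setting.** Also correct. Neighbouring sites may well be more alike than distant ones. The third puncture segment starts at 10 cm, so a scan of that length at 2 cm spacing would have more than 5 sites. With 8 sites and AR(1), the gap is 3 to 17 points, and at 0.6 SD it is small everywhere.

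4. **Between-groups ANOVA may be meant for the puncture outcomes.** It can suit puncture time if each patient has one puncture. That use is not in question.

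A reader might also infer that reporting mean ± SD is itself an error, because it does not show how often the nerve lies close to the artery. The SAP does not support that. It does not limit reporting to mean ± SD, it allows "count data are presented as example or percentage", and it states no rule that ranks sites by nerve distance. Any figure for the share of close nerves would need an invented mean, SD and cut-off. Low percentiles and minima are a reporting option.

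**Conclusion.** The point holds as a minor one. For comparisons of ultrasound readings between sites or arms, the method in section Xi has the wrong error term. In the settings simulated, it rejects in about 0% to 4% of null cases instead of 5%. With 85 patients, 5 sites and a 0.3 SD drift, it has about 10% to 33% power, against 40% to 90%.

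The direction follows from any positive within-patient correlation. The size rests on assumed site numbers, correlations and drift, and on the inference that sites and arms repeat within patients.

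Two stronger readings go too far:

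- That real anatomical differences would generally be missed. The loss is material only for small differences.
- That the choice of puncture site is compromised. Research methods (section 3, item 2) speaks of choosing an optimal position after the scan, but gives no rule that ties the choice to this test, and the study steps have the puncture site picked at random.

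Comparisons by age, BMI or sex are outside the point, because the SAP does not say how a patient's several readings would be combined for them.

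**What to change.** In section Xi, add that ultrasound measurements are compared across the 2 cm sites and between arms with a mixed model with a patient effect (arm nested within patient). Repeated-measures ANOVA with Greenhouse-Geisser correction is an acceptable alternative, with a paired test for left v right at a single site. Keep between-groups ANOVA for continuous puncture outcomes with one puncture per patient.

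The cost is one changed sentence. The same readings and the same software (SPSS 22.0) suffice, with no extra scan or patient. Adding the median, low percentiles and minimum of the nerve distance per site is optional.

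### Count outcomes are given a two-group t test, so three or six puncture sites have no overall comparison; unadjusted pairwise use would make false site differences about 2.5 to 7 times too frequent at event rates of 10-90%

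*SAP*

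**What the plan says.** Section Xi of the SAP is the whole of its analysis text. Measurement data are to be given as mean and standard deviation and compared between groups by ANOVA. For the other kind of outcome it says "count data are presented as example or percentage, with t test", with P < 0.05 as the criterion. It names no chi-square, exact or other test for proportions, and no adjustment for multiple comparisons.

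The outcomes this rule must serve are in section 3, under Study steps. There "the radial artery surface projection was divided into three sections", and then "the puncture site was divided into the first stage of the left hand, the second section of the left hand", and so on through both hands, which makes six sites. For assignment, "the experimenter randomly selected the puncture site". At these sites "the first puncture success rate, puncture insertion time and puncture times were recorded", together with puncture-related complications. The secondary objective in section 2 is "To find the best site of radial artery puncture to improve the safety and accuracy of radial artery puncture and catheterization".

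**The concern.** First-puncture success and complications are yes/no outcomes over more than two sites. A t test takes two groups at a time and is not the standard test for proportions. The same section gives continuous data an overall multi-group test but gives count data none.

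The SAP does not say how a two-group test is to be applied across three or six sites. The most direct way to follow it is to test every pair, each at 0.05. A pair of sites could then be reported as different, and one of them favoured, when a single test of all sites shows no difference. This bears on the objective of choosing a site. It does not touch the anatomical main objective, whose measurements fall under ANOVA.

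**Working it through.** **Inputs from the SAP.** Total of 100 patients and 15% loss (section 3); three segments or six segment-by-hand sites (section 3, Study steps); threshold 0.05 (section Xi).

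**Assumptions.** The SAP gives no allocation ratio and no event rates. Near-equal groups are assumed: 34/33/33, or 17/17/17/17/16/16. Tests are two-sided, the t test is pooled on 0/1 data, and the true rate is the same at every site.

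**Number of pairs.** k(k - 1)/2 gives 3 x 2/2 = 3 for three segments and 6 x 5/2 = 15 for six sites.

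**Is a single t test the problem?** Take 17/17 against 13/17.
- t test: the pooled variance is (0 + 17 x 0.7647 x 0.2353)/32 = 0.0956. The standard error is the square root of 0.0956 x 2/17, which is 0.106. So t = 0.2353/0.106 = 2.22 on 32 df, p = 0.034.
- Pearson chi-square: 34 x (17 x 4 - 0 x 13)^2/(17 x 17 x 30 x 4) = 4.53, p = 0.033.

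Over all possible 17 v 17 and 33 v 33 tables, the two tests never disagree at 0.05. One pair is therefore not the fault.

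**Chance of at least one false pair, no true difference, N = 100.** The three-segment figures are exact enumerations; the six-site figures come from 200,000 simulated trials per rate.

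| True rate | Three segments: any pair by t test | Three segments: one overall chi-square | Six sites: any pair by t test | Six sites: one overall chi-square |
|---|---|---|---|---|
| 5% | 8.4% | 3.7% | 4.5% | 4.1% |
| 10% | 12.5% | 4.3% | 25.0% | 4.4% |
| 20% | 12.9% | 4.9% | 34.1% | 4.7% |
| 30% | 12.6% | 5.0% | 33.7% | 4.8% |
| 50% | 13.3% | 5.0% | 34.8% | 5.0% |

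Rates of 70, 80, 90 and 95% mirror 30, 20, 10 and 5%. Against the nominal 5%, the factor runs from 12.5/5 = 2.5 to 34.8/5 = 7.0 over rates of 10-90%. At a 2% rate the pairwise figures fall to about 1% and 0.2%.

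**After 15% loss.** 100 x 0.85 = 85 patients. The pairwise figures are 11.9-13.8% (29/28/28) and 18-37% (15, then five groups of 14) at rates of 10-90%.

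**Illustration, six sites.** Successes of 17/17, 15/17, 15/17, 13/17, 14/16 and 14/16 make 88 of 100. The first against the fourth site gives t-test p = 0.034. The overall chi-square is 4.47 on 5 df, p = 0.48, and the Fisher-Freeman-Halton p is also 0.48. Holm gives 15 x 0.0337 = 0.51.

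**Illustration, three segments.** Successes of 33/34, 30/33 and 27/33 give t-test p = 0.042 for first against third. The overall chi-square is 4.37 on 2 df, p = 0.11, and the exact p is 0.096. Holm gives 3 x 0.042 = 0.13.

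**The case against.** Several points can fairly be put in the plan's defence.

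- **The inflation comes from multiplicity, not from the t test itself.** This is true. Unadjusted pairwise chi-square tests would inflate just as much. So changing only the name of the test would not be enough.
- **Pairwise testing is inferred.** The SAP does not state it, so the error rates are conditional on that use. The absence of any overall test for proportions is not conditional.
- **Three segments is the likelier reading.** Sections 3 and Vi describe the comparison by distance along the forearm. On that reading the factor is 2.5-2.7 (12.5/5 to 13.3/5), and the upper figure of 7 applies only if all six sites are compared. The SAP leaves this open.
- **The event rates are assumed.** If complications are rare, or first-puncture success is about 95%, there is much less inflation with three segments (8.4% at a 5% or 95% rate) and none with six sites (4.5%). This stands as a limit on the size.
- **The three-segment illustration is not a proven false positive.** Success falls steadily along ordered segments, and a Cochran-Armitage trend test gives p = 0.038. The example shows only that a pairwise and an overall reading can conflict.
- **Holm is more than three segments need.** An overall chi-square test followed by unadjusted pairs already keeps false differences to 4.1-5.0% there at rates of 10-90%. This is correct for three groups, but six sites are still open under the SAP.
- **The text looks machine-translated.** The test name may be a slip. Even so, the text at hand specifies a t test, and correcting the name would leave the multi-site comparison unspecified.

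These points narrow the size of the problem. None supplies the missing comparison.

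**Conclusion.** The concern holds. As written, the SAP has no valid overall comparison of first-puncture success or complications across sites and no control of multiple comparisons, although these outcomes help to choose the best site.

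Used pairwise without adjustment, the stated rule raises the chance of a false site difference to 12.5-13.3% (three segments) or 25-35% (six sites). This rests on 100 patients, near-equal groups, no true difference and rates of 10-90%. The size is therefore conditional; the gap in the plan is not. It should be fixed before analysis, but it concerns the secondary objective only.

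**What to change.** In section Xi, replace the t test for count data with wording such as:

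> First-puncture success and puncture-related complications are compared across sites by one overall chi-square test, or by the Fisher-Freeman-Halton exact test when any expected count is below 5. Only if this test has P < 0.05 are pairs of sites compared, with Holm-adjusted P values. Differences in proportions are reported with 95% confidence intervals (for example Newcombe).

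The exact test will often be needed with six sites: at a 10% or 90% rate, the smaller expected count with 17 patients is 17 x 0.10 = 1.7.

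Also state whether the overall comparison is of three segments or six segment-by-hand sites, since this sets the follow-up pairs at 3 or 15. Say too which rule covers the number of punctures, which could be read as either kind of data.

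With Holm-adjusted pairwise Fisher tests, the chance of any false pair is at most 3.4% (three segments) and 1.8% (six sites) over rates of 5-95%.

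The cost is a few sentences, with no new data or patients. Some p-values become less favourable: Holm multiplies the smallest by 3 or by 15. Apparent power also falls. At assumed true rates of 95/80/80% in three segments, the chance of any significant pair is 67% with unadjusted pairs, 43% with the overall test first, and 39% with the overall test and Holm-adjusted Fisher pairs. If only three segments are compared, the overall test followed by unadjusted pairs is a defensible, less conservative alternative.
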